## **13. TRIAL MANAGEMENT**

### **13.1. Data Reporting**

#### **13.1.1. Method**

The Office of Data Quality (ODQ) will collect, manage, and monitor data for this study.

#### **13.1.2. Data Submission**

Investigative sites within DF/HCC or DF/PCC are responsible for submitting data and/or data forms to the Office of Data Quality (ODQ) in accordance with DF/HCC policies.

The schedule for completion and submission of case report forms (paper or electronic) is as follows:

Form	Submission Timeline
Eligibility Checklist	Complete prior to registration in OnCore
On Study Form	Within 14 days of registration
Baseline Assessment Form	Within 14 days of registration
Treatment Form	Within 10 days of the last day of the cycle
Adverse Event Report Form	Within 10 days of the last day of the cycle
Response Assessment Form	Within 10 days of the completion of the cycle required for response evaluation
Follow up/Survival Form	Within 14 days of the protocol defined follow up visit date or call

When a participant is removed from protocol therapy and/or is off of the study, the relevant Off-Treatment/Off-Study information will be updated in OnCore.

### **13.2. Data Safety Monitoring**

The DF/HCC Data and Safety Monitoring Committee (DSMC) will review and monitor toxicity and accrual data from this study. The committee is composed of medical oncologists, research nurses, pharmacists and biostatisticians with direct experience in cancer clinical research. Information that raises any questions about participant safety will be addressed with the Overall PI and study team.

The DSMC will review each protocol up to four times a year with the frequency determined by the outcome of previous reviews.. Information to be provided to the committee may include: up-to-date participant accrual; current dose level information; DLT information; all grade 2 or higher unexpected adverse events that have been reported; summary of all deaths occurring within 100 days of intervention; for gene therapy protocols, summary of all deaths while being treated and during active follow-up; any response information; audit results, and a summary provided by the study team. Other information (e.g. scans, laboratory values) will be provided upon request.

### **13.3. Compliance with Trial Registration and Results Posting Requirements**

Under the terms of the Food and Drug Administration Modernization Act (FDAMA) and the Food and Drug Administration Amendments Act (FDAAA), the sponsor-investigator of the trial is solely responsible for determining whether the trial and its results are subject to the requirements for submission to the Clinical Trials Data Bank, <http://www.clinicaltrials.gov>. All results of primary and secondary objectives must be posted to CT.gov within a year of completion. Information posted will allow subjects to identify potentially appropriate trials for their disease conditions and pursue participation by calling a central contact number for further information on appropriate trial locations and study site contact information.

## **14. ETHICS**

### **14.1. Ethical Conduct of the Study**

The study will be performed in accordance with ethical principles originating from the Declaration of Helsinki. Conduct of the study will be in compliance with ICH Good Clinical Practice, and with all applicable federal (including 21 CFR parts 56 & 50), state, or local laws, as well as DF/HCC research policies and procedures (<http://www.dfhcc.harvard.edu/clinical-research-support/clinical-research-unit-cru/policies-and-procedures/>).

### **14.2. Informed Consent Process**

The site investigator will ensure the subject is given full and adequate oral and written information about the nature, purpose, possible risks and benefits of the study. Subjects must also be notified they are free to discontinue from the study at any time. The subject should be given the opportunity to ask questions and allowed time to consider the information provided.

The subject's signed and dated informed consent must be obtained before conducting any procedure specifically for the study. The site investigator must store the original, signed informed consent form. A copy of the signed informed consent form must be given to the subject.

### **14.3. Human Subject Protections**

#### **14.3.1. Rationale for Subject Selection**

##### **14.3.1.1. Selection Based on Gender, Ethnicity, and Race**

Subjects from all racial/ethnic groups are eligible for this study if they meet the eligibility criteria. To date, there is no information that suggests that differences in drug metabolism or disease response would be expected in one group compared with another. Efforts will be made to extend accrual to a representative population, but in this preliminary study, a balance must be struck between patient safety considerations and limitations on the number of individuals exposed to potentially toxic and/or ineffective treatments on one hand and the need to explore ethnic aspects of clinical research on the other hand. If differences in outcome that correlate with ethnic identity are noted, accrual may be expanded or a follow-up study may be written to investigate those differences more fully. Women are not eligible for this study as this disease occurs only in men.

#### **14.3.1.2. Strategies/Procedures for Recruitment**

Patient accrual for this protocol will consist of outreach to medical oncologists caring for patients at DFHCC. We will also reach out to the Boston Prostate Cancer Support Group with information for interested patients. This protocol will be listed on [www.clinicaltrials.gov](http://www.clinicaltrials.gov).

#### **14.3.1.3. Justification for Exclusions**

Due to impaired cellular immunity, this protocol excludes patients with chronic viral infections including HIV, HBV, and HCV.

#### **14.3.1.4. Participation of Children**

Men under the age of 18 will not be eligible for participation in this study based on the fact that patients under 18 are unlikely to have PCa and the toxicities of nivolumab in pediatric patients is unknown.

### **14.3.2. Evaluation of Benefits/Risks/Discomforts**

There is no firmly established standard-of-care therapy for patients with PCa and rising PSA following local definitive therapy. Potential risks of nivolumab and in this patient population include the range of side effects outlined in section 10.1.8.

#### **14.3.2.1. Procedures to Eliminate or Minimize Potential Risks**

All patients will be given blood tests, physical examinations, and scans, as described in the study calendar (section 7), and must have a local physician to provide long-term care and monitoring for complications. No compensation is available, but any injury will be evaluated and treated in keeping with the benefits or care to which patients are entitled under applicable regulations.

### 14.3.2.2. Provisions for Monitoring Data Collection to Ensure Subject Safety

As information is gathered from this trial, clinical results will be shared with patients. Laboratory and clinical data will be frequently gathered and any new significant finding(s) found during the course of the research, which may affect a patient's willingness to participate further, will be explained.

Confidentiality of information concerning participants will be maintained, including in all publications and presentations resulting from this study. Names of participants or material identifying participants will not be released without permission, except as such release is required by law. Records at the National Cancer Institute are maintained according to current legal requirements, and are made available for review, as required by the Food and Drug Administration or other authorized users, only under the guidelines established by the Federal Privacy Act.

## 16. APPENDICES

**Appendix 1: Management of immune-related Adverse Events**

**Appendix 2: Information sheet for shipment of preliminary PD-L1-positive cases**

**Appendix 3: Instructions for peripheral blood collection for exploratory studies**

## Appendix 1: Management of Immune-Related Adverse Events

Immune-related adverse reaction	Severity	Treatment modification
Immune-related pneumonitis	Grade 2 pneumonitis	Withhold dose(s) until symptoms resolve, radiographic abnormalities improve, and management with corticosteroids is complete
	Grade 3 or 4 pneumonitis	Permanently discontinue treatment
Immune-related colitis	Grade 2 diarrhoea or colitis	Withhold dose(s) until symptoms resolve and management with corticosteroids, if needed, is complete
	Grade 3 diarrhoea or colitis	Withhold dose(s) until symptoms resolve and management with corticosteroids is complete
	Grade 4 diarrhoea or colitis	Permanently discontinue treatment
Immune-related hepatitis	Grade 2 elevation in aspartate aminotransferase (AST), alanine aminotransferase (ALT), or total bilirubin	Withhold dose(s) until laboratory values return to baseline and management with corticosteroids, if needed, is complete
	Grade 3 or 4 elevation in AST, ALT, or total bilirubin	Permanently discontinue treatment
Immune-related nephritis and renal dysfunction	Grade 2 or 3 creatinine elevation	Withhold dose(s) until creatinine returns to baseline and management with corticosteroids is complete
Immune-related endocrinopathies	Grade 4 creatinine elevation	Permanently discontinue treatment
	Symptomatic Grade 2 or 3 hypothyroidism, hyperthyroidism, hypophysitis, Grade 2 adrenal insufficiency, Grade 3 diabetes	Withhold dose(s) until symptoms resolve and management with corticosteroids (if needed for symptoms of acute inflammation) is complete. Treatment should be continued in the presence of hormone replacement therapy a as long as no symptoms are present
	Grade 4 hypothyroidism, Grade 4 hyperthyroidism, Grade 4 hypophysitis, Grade 3 or 4 adrenal insufficiency, Grade 4 diabetes	Permanently discontinue treatment
	Grade 3 rash	Withhold dose(s) until symptoms resolve and management with corticosteroids is complete
	Grade 4 rash	Permanently discontinue treatment
Immune-related skin adverse reactions	Stevens-Johnson syndrome (SJS) or toxic epidermal necrolysis (TEN)	Permanently discontinue treatment
	Grade 3 (first occurrence)	Withhold dose(s)
	Grade 3 myocarditis	Permanently discontinue treatment
Other immune-related adverse reactions	Grade 4 or recurrent Grade 3 ; persistent Grade 2 or 3 despite treatment modification ; inability to reduce	Permanently discontinue treatment

## GI Adverse Event Management Algorithm

[figure not shown]
Rule out non-inflammatory causes. If non-inflammatory cause is identified, treat accordingly and continue I-O therapy. Opiates/narcotics may mask symptoms of perforation. Infliximab should not be used in cases of perforation or sepsis.

Grade of Diarrhea/ Colitis (NCI CTCAE v4)	Management	Follow-up
Grade 1 Diarrhea: < 4 stools/day over baseline; Colitis: asymptomatic	
 
Continue I-O therapy per protocol
 
Symptomatic treatment
 
	
 
Close monitoring for worsening symptoms.
 
Educate patient to report worsening immediately
 
If worsens:
 
Treat as Grade (G) 2 or 3/4
 

Grade 2 Diarrhea: 4-6 stools per day over baseline; IV fluids indicated <24 hours (hrs); not interfering with ADL Colitis: abdominal pain; blood in stool	
 
Delay I-O therapy per protocol
 
Symptomatic treatment
 
	
If improves to grade 1:
 
 
Resume I-O therapy per protocol
 
 
If persists > 5-7 days or recurs:
 
 
0.5-1.0 mg/kg/day methylprednisolone or oral equivalent
 
When symptoms improve to grade 1, taper steroids over at least 1 month, consider prophylactic antibiotics for opportunistic infections, and resume I-O therapy per protocol.
 
 
If worsens or persists > 3-5 days with oral steroids:
 
 
Treat as grade 3/4
 

Grade 3-4 Diarrhea (G3): ≥7 stools per day over baseline; incontinence; IV fluids ≥24 hrs; interfering with activities of daily living (ADL) Colitis (G3): severe abdominal pain, medical intervention indicated, peritoneal signs G4: life-threatening, perforation	
 
Discontinue I-O therapy per protocol
 
1.0 to 2.0 mg/kg/day methylprednisolone IV or IV equivalent
 
Add prophylactic antibiotics for opportunistic infections
 
Consider lower endoscopy
 
	
If improves:
 
 
Continue steroids until grade 1, then taper over at least 1 month
 
 
If persists > 3-5 days, or recurs after improvement:
 
 
Add infliximab 5 mg/kg (if no contraindication).
 
 
Note: Infliximab should not be used in cases of perforation or sepsis

Patients on IV steroids may be switched to an equivalent dose of oral corticosteroids (e.g. prednisone) at start of tapering or earlier, once sustained clinical improvement is observed. Lower bioavailability of oral corticosteroids should be taken into account when switching to the equivalent dose of oral corticosteroids.

## Renal Adverse Event Management Algorithm

[figure not shown]
Rule out non-inflammatory causes. If non-inflammatory cause, treat accordingly and continue I-O therapy

Patients on IV steroids may be switched to an equivalent dose of oral corticosteroids (e.g. prednisone) at start of tapering or earlier, once sustained clinical improvement is observed. Lower bioavailability of oral corticosteroids should be taken into account when switching to the equivalent dose of oral corticosteroids.

## Pulmonary Adverse Event Management Algorithm

[figure not shown]
Rule out non-inflammatory causes. If non-inflammatory cause, treat accordingly and continue I-O therapy. Evaluate with imaging and pulmonary consultation.

Patients on IV steroids may be switched to an equivalent dose of oral corticosteroids (e.g. prednisone) at start of tapering or earlier, once sustained clinical improvement is observed. Lower bioavailability of oral corticosteroids should be taken into account when switching to the equivalent dose of oral corticosteroids.

## Hepatic Adverse Event Management Algorithm

Rule out non-inflammatory causes. If non-inflammatory cause, treat accordingly and continue I-O therapy. Consider imaging for obstruction.

[figure not shown]
Patients on IV steroids may be switched to an equivalent dose of oral corticosteroids (e.g. prednisone) at start of tapering or earlier, once sustained clinical improvement is observed. Lower bioavailability of oral corticosteroids should be taken into account when switching to the equivalent dose of oral corticosteroids.

\*I-O therapy may be delayed rather than discontinued if AST/ALT ≤ 8 x ULN and T.bili ≤ 5 x ULN.

\*\*The recommended starting dose for grade 4 hepatitis is 2 mg/kg/day methylprednisolone IV.

## Endocrinopathy Management Algorithm

[figure not shown]
Rule out non-inflammatory causes. If non-inflammatory cause, treat accordingly and continue I-O therapy. Consider visual field testing, endocrinology consultation, and imaging.

Patients on IV steroids may be switched to an equivalent dose of oral corticosteroids (e.g. prednisone) at start of tapering or earlier, once sustained clinical improvement is observed. Lower bioavailability of oral corticosteroids should be taken into account when switching to the equivalent dose of oral corticosteroids.

## Skin Adverse Event Management Algorithm

Rule out non-inflammatory causes. If non-inflammatory cause, treat accordingly and continue I-O therapy.

[figure not shown]

Patients on IV steroids may be switched to an equivalent dose of oral corticosteroids (e.g. prednisone) at start of tapering or earlier, once sustained clinical improvement is observed. Lower bioavailability of oral corticosteroids should be taken into account when switching to the equivalent dose of oral corticosteroids.

\*Refer to NCI CTCAE v4 for term-specific grading criteria.

# Neurological Adverse Event Management Algorithm

Rule out non-inflammatory causes. If non-inflammatory cause, treat accordingly and continue I-O therapy.

Patients on IV steroids may be switched to an equivalent dose of oral corticosteroids (e.g. prednisone) at start of tapering or earlier, once sustained clinical improvement is observed. Lower bioavailability of oral corticosteroids should be taken into account when switching to the equivalent dose of oral corticosteroids.

**SEND BACK TO RESEARCH FACILTY**\_\_\_\_\_ **READ AT**  
**ACUPATH**\_\_\_\_\_  
**ANY OTHER REQUIREMENTS:**

**RESEARCH ID INFORMATION** \_\_\_\_\_

**COMMENTS:**

**ACUPATH ACCESSION NUMBER** \_\_\_\_\_

### Appendix 3: Instructions for peripheral blood collection for exploratory studies

As outlined in the study calendar (section 7), peripheral blood collections will be mandatory for subjects participating in this study.

- Cycle 1 day 1:
  - 5-10 mL in one 10-mL EDTA (purple top) tube at room temperature for germline WES
    - Email [name] ([[contact]](mailto:[contact])) in advance to notify [name] lab of collection
    - For DFCI patients, email BIDMC CRAs ([[contact]](mailto:[contact])) one week in advance to arrange collection
  - 30 mL in three-to-four 10-mL EDTA tubes at room temperature for soluble biomarkers and immunophenotyping
    - Email [name] ([[name]\\[contact]](mailto:[contact])) one week to notify Immune Assessment lab of collection
    - For BIDMC patients, blood will need to be brought to the Immune Assessment Lab by a BI CRA
    - For DFCI patients, blood can be sent via tube system
- Cycle 2 day 1 and End-of-Treatment visit, plus optional collection at 1 week after cycle 1:
  - 30 mL in three-to-four 10-mL EDTA tubes at room temperature for soluble biomarkers and immunophenotyping
    - Email [name] ([[name]\\[contact]](mailto:[contact])) one week to notify Immune Assessment lab of collection
    - For BIDMC patients, blood will need to be brought to the Immune Assessment Lab by a BI CRA
    - For DFCI patients, blood can be sent via tube system
- Cycle 5 day 1 and q4 cycles beyond (cycle 9 day 1, cycle 13 day 1, etc.):
  - 80 mL TOTAL in eight-to-eleven 10-mL EDTA tubes at room temperature, divided as follows:
    - 50 mL in five-to-seven 10-mL EDTA tubes at room temperature for PBMC banking for assessment of T-cell responsiveness to neoantigens
      - Email [name] ([[contact]](mailto:[contact])) in advance to notify [name]/[name] lab of collection
      - For DFCI patients, email BIDMC CRAs ([[contact]](mailto:[contact])) one week in advance to arrange collection
    - 30 mL in three-to-four 10-mL EDTA tubes at room temperature for soluble biomarkers and immunophenotyping PLUS PMBC banking for assessment of T-cell responsiveness to neoantigens
      - Email [name] ([[name]\\[contact]](mailto:[contact])) one week to notify Immune Assessment lab of collection

- For BIDMC patients, blood will need to be brought to the Immune Assessment Lab by a BI CRA
- For DFCI patients, blood can be sent via tube system

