### **2.1.3. Exploratory Objectives**

- Evaluate whether response to nivolumab treatment is enriched among patients with tumor programmed death-ligand 1 (PD-L1) expression on tumor cells and on tumor-infiltrating lymphocytes and antigen-presenting cells (APCs)
- Identify genomic biomarkers associated with response to nivolumab
- Evaluate correlations between alterations in DNA-damage-repair genes and PD-L1 expression
- Evaluate correlations between tumor-infiltrating lymphocytes and APCs with response to nivolumab
- Evaluate subtypes of “exhausted” tumor-infiltrating lymphocytes
- Explore whether peripheral T-cells are present that might recognize tumor neoantigens and whether these correlate with responses to nivolumab
- Assess for genomic alterations in circulating tumor DNA and correlate with mutations identified in primary tumor specimens
- Assess levels of plasma cytokines prior to initiation and during therapy and determine whether levels or changes in specific cytokines may be predictive biomarkers for response
- Assess PBMC subsets prior to initiation and during therapy and determine basal features or changes during therapy may be predictive biomarkers for response

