## **5.2. Nivolumab Administration**

Nivolumab will be given on day 1 of a 28-day cycle at a dose of 480 mg intravenously (IV). All visits have a window of +/- 3 days (see Study Calendar, section 7).

The administration of nivolumab infusion must be completed within 24 hours of preparation. If not used immediately, the infusion solution may be stored under refrigeration conditions (2°C to 8°C, 36°F to 46°F) for up to 24 hours, and a maximum of 8 hours of the total 24 hours can be at room temperature (20°C to 25°C, 68°F to 77°F) and room light. The maximum of 8 hours under room temperature and room light conditions includes the product administration period. The unopened vials can be stored at room temperature (up to 25°C, 77°F) and room light for up to 48 hours.

Nivolumab injection is to be administered as an IV infusion over 30 minutes (acceptable window is 25 minutes to 40 minutes) through a 0.2-micron to 1.2-micron pore size, low-protein binding (polyethersulfone membrane) in-line filter at the protocol-specified doses

and infusion times. It is not to be administered as an IV push or bolus injection. Nivolumab can be infused undiluted or diluted so as not to exceed a total infusion volume of 160 mL. For patients weighing less than 40 kilograms (kg), the total volume of infusion must not exceed 4 mL per kg of patient weight.

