Third, we will consider exploratory analyses of tumor neoantigens and peripheral T-cell reactivity. Whole-exome sequencing (WES) of primary tissue may be used to identify potential tumor neoantigens that could be the target of effector T-cell responses. Sequential peripheral blood collections will allow banking of antigen-presenting cells and T-cells. If there are patients with strong responses to nivolumab treatment, we will consider evaluating their banked samples for evidence of T-cell responsiveness to the potential neoantigens identified in the patients' primary tumor WES data.

Fourth, banked blood would allow future analysis of circulating tumor DNA to investigate whether mutations in the primary tissue correlated with mutations at the time of biochemical recurrence.

Finally, we will assess changes in soluble biomarkers (cytokines, chemokines) during treatment, which may correlate with treatment response.

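### Blood for neoantigen T-cell testing is designated only from cycle 5 (week 16), so any comparison with response is limited to men still on treatment and has no baseline

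*Combined protocol and SAP*

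**What the plan says.** The exploratory objective in Section 2.1.3 reads: "Explore whether peripheral T-cells are present that might recognize tumor neoantigens and whether these correlate with responses to nivolumab". Three other sections describe the same work, each more narrowly:

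- Section 2.2.3 lists an endpoint of detecting such cells and does not mention response.
- Section 8.1 says "Sequential peripheral blood collections will allow banking of antigen-presenting cells and T-cells". It then says only that the team will consider testing banked samples from patients with strong responses.
- Section 12.3 relates markers to disease control. Its examples are PD-L1, CD8+ TILs, plasma cytokines and PBMC subsets. Neoantigen-reactive T-cells are not among them, although the list is given as examples.

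Appendix 3 assigns the blood:

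- Cycle 1 day 1: "5-10 mL in one 10-mL EDTA (purple top) tube at room temperature for germline WES", and "30 mL in three-to-four 10-mL EDTA tubes at room temperature for soluble biomarkers and immunophenotyping".
- "Cycle 2 day 1 and End-of-Treatment visit, plus optional collection at 1 week after cycle 1": the same 30 mL, for the same two uses.
- Cycle 5 day 1 and every fourth cycle after: 80 mL, made up of "50 mL in five-to-seven 10-mL EDTA tubes at room temperature for PBMC banking for assessment of T-cell responsiveness to neoantigens" and a further 30 mL that serves biomarkers, immunophenotyping and also PBMC banking for the neoantigen work.

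The Section 7 calendar agrees: research blood at cycles 1, 2, 5, 9 and so on, and at End of Study (taken here to be Appendix 3's End-of-Treatment visit), with none at cycles 3 or 4. Footnote g allows research blood to be taken before or after the infusion in some circumstances. Section 8.3 keeps whatever is not used up.

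**The concern.** A correlation with response needs cells from men who did and did not respond, collected in a way that does not depend on the outcome. Here the first designated collection comes after the week-12 endpoint and only in men who are still being treated. Whether a man contributes a sample can therefore depend on how he did. A man who leaves at or before week 12 has no blood designated for this objective at any time, because his exit draw is assigned to other uses.

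The missing baseline is a separate problem and affects everyone. All designated samples are taken on treatment, so reactivity found at week 16 cannot be compared with the same man's status before dosing. An association with response could not be read as predictive. This holds even for the strong responders whom Section 8.1 has in mind. A pre-treatment sample cannot be obtained later.

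**Working it through.** **Timing.** Section 5.2: "Nivolumab will be given on day 1 of a 28-day cycle". Day of cycle k = 28 × (k − 1) + 1.

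- Cycle 4 day 1 = 28 × 3 + 1 = day 85, which is 12 weeks after the first dose (the primary endpoint).
- Cycle 5 day 1 = 28 × 4 + 1 = day 113, which is 16 weeks.
- The first designated banking is 4 weeks after the endpoint.

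**Is the appendix entry intact?** At cycle 5 the volumes add up (50 + 30 = 80 mL), and so do the tubes (5 + 3 = 8 to 7 + 4 = 11). The 30 mL line at cycle 5 adds PBMC banking to its uses; the corresponding line at the earlier visits and at End-of-Treatment does not. The gap belongs to the schedule and is not lost text.

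| Visit | Designated for neoantigen banking |
|---|---|
| Cycle 1 day 1 | none |
| Optional week 1, cycle 2 day 1 | none |
| Cycles 3 and 4 | no research blood |
| Cycle 5, 9, 13 and so on | 50 mL, plus 30 mL shared |
| End-of-Treatment | none |

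**Design rates.** Section 12.1 is used here only to count men with and without disease control. Its figures reproduce closely enough for that:

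- PD-L1-positive, at least 2 of 20: 1 − (1 − p)^20 − 20p(1 − p)^19 gives power 0.976 at p = 0.25 (stated 97%) and alpha 0.0169 at p = 0.01 (stated 0.02).
- PD-L1-negative, at least 1 of 14: 1 − (1 − p)^14 gives power 0.956 at p = 0.20 (stated 96%) and alpha 0.131 at p = 0.01 (stated 0.13).

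**Expected counts.**

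- At the design rates: controlled = 20 × 0.25 + 14 × 0.20 = 5 + 2.8 = 7.8; not controlled = 34 − 7.8 = 26.2.
- At the null rate: controlled = 34 × 0.01 = 0.34; not controlled = 33.66.

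Let f be the share of non-controlled men still on treatment at cycle 5. The documents do not give f, so the whole range is shown as an assumption. Men sampled = f × (number not controlled).

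| f | Design rates: sampled | Design rates: not sampled | Null rate: sampled |
|---|---|---|---|
| 0 | 0 | 26.2 | 0 |
| 0.25 | 6.55 | 19.65 | 8.4 |
| 0.50 | 13.1 | 13.1 | 16.8 |
| 0.75 | 19.65 | 6.55 | 25.2 |
| 1 | 26.2 | 0 | 33.7 |

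If all 7.8 controlled men reach cycle 5, the two groups are equal in size at f = 7.8 / 26.2 = 0.30. Controlled men are the larger group only if more than about 70% of non-controlled men have stopped.

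Designated pre-treatment samples are 0 of 34 for every f.

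**The case against.** The strongest reply is that the schedule fits what Section 8.1 actually undertakes. That section makes the work conditional on responses, calls it hypothesis-generating, and names only strong responders, who should reach cycle 5 unless toxicity stops them. Section 2.2.3 asks only for detection, and no section sets out to show that the drug induced the cells. In addition, 30 mL is drawn from every treated man at cycle 1, and Section 8.3 stores leftovers.

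Much of this stands. A reader might infer that the comparison with response cannot be made at all, or that the banked men would mostly be those with disease control. The documents support neither. The synopsis lets men with isolated PSA progression at week 12 continue at the investigator's discretion, and PSA rise is not among the reasons for stopping in Section 6.7. Non-controlled men may therefore reach cycle 5, and at f = 0.50 they would outnumber the controlled men. Nor do the documents amount to a committed correlation analysis: the wish is in Section 2.1.3, and the other sections promise less.

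Two parts of the reply do not close the gap. Storing leftovers does not assure viable T-cells, and footnote g does not assure that cycle 1 blood is taken before the infusion. Section 2.1.3 also still names correlation with response, which the collection schedule serves poorly.

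**Conclusion.** The point holds in a limited form. The neoantigen objective has no designated pre-treatment or End-of-Treatment T-cell bank. A comparison with response remains possible, but it would be selected on continuing treatment to week 16 and would lack a baseline.

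The absence of a designated baseline applies to all 34 men and rests on no assumption. The loss of non-controlled men does rest on one: it runs from 0 to about 26 of 26 at the design rates, and nothing in the documents narrows that range. It would also be too strong to say that men who leave early have no blood at all. They have immunophenotyping blood, but none designated for this use.

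The objective is exploratory. No primary, secondary or safety analysis is affected. The change is still worth making because it is cheap and cannot be made for a man once he has been dosed.

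**What to change.** 1. **Appendix 3.** Extend the added PBMC-banking use, already written for the 30 mL at cycle 5, to the 30 mL drawn at cycle 1 day 1 and at End-of-Treatment. Residual viable PBMCs would then be banked before dosing and at exit, whether or not a man stays on treatment.
2. **Cycle 1 timing.** State in Appendix 3 and footnote g of Section 7 that the cycle 1 day 1 research blood is taken before the infusion.
3. **Reconcile Sections 2.1.3, 2.2.3, 8.1 and 12.3** on whether a correlation with response is intended. If it is not, reduce the objective to detection. If it is, say in Section 8.1 that the banked samples chosen for testing will come from both responders and non-responders, each paired with the man's own baseline.

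Steps 1 and 2 add no visit, needle stick or blood volume. They cost extra processing and freezer space, and the residual cell yield from 30 mL may be limited. If a correlation is kept under step 3, each non-responder tested adds tumour exome sequencing and T-cell assays, so how many to test should stay optional. A new 50 mL draw at cycle 1 is not proposed: it would take more blood from every man, and moving a cycle 13 draw would not offset it, since only men treated for 48 weeks reach that visit.
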